6.2 DETAILS OF TRIAL PROCEDURES AT SELECTED VISITS

6.2.1 Screening

After having been informed about the trial, all subjects will provide written informed consent in accordance with GCP and local legislation prior to enrolment in the trial.

For information regarding laboratory tests (including drug and virus screening), ECG, vital signs, and physical examination, refer to Sections [5.2.1](#) to [5.2.5](#).

Re-screening of individual subjects is allowed during the screening period as per the investigator's discretion. In such a case only the final re-screening results will be recorded in the eCRF. Initial screening results will be recorded in the subject's medical file.

6.2.2 Treatment period

Each subject will participate in one of the two treatment periods.

On Day -1, trial participants will be admitted to the trial site and kept under close medical surveillance for 24 h following the administration of trial medication in the morning of Day 1. The subjects will continue to stay on site and have further samples taken until discharge on Day 10 as indicated in the [Flow Chart](#). Then they will be allowed to leave the trial site.

Note: For subjects in the additional microtracer cohort (2b) aimed at repeating blood sampling for plasma metabolite profiling and secondary endpoints, the following release criteria do not apply.

In those cohorts assessing release criteria (cohort 1 and 2a), a subject's individual end of study will vary depending on when the release criteria for radioactive recovery are met.

If release criteria have not been met (refer to section [3.1](#) for definition) at Day 10 (initial discharge), subjects will be readmitted to the trial site for up to three additional 24 h in-house periods for the collection of urine and faeces, 1, 2 and 3 weeks after the initial discharge, respectively. Within 24 h prior to each of these once-weekly in-house sampling periods, subjects are to collect faeces at home. These home collections will be used as a back-up option for analysis in case no defaecation occurs in the subsequent 24 h in-house collection period. If faeces are collected in the subsequent in-house collection period, the faeces previously collected at home will be discarded.

Once release criteria are met, the home collections of faeces and additional in-house sampling of urine and faeces will be stopped. If a subject is unable to attend one of these additional in-house sampling visits, they may be allowed to reschedule the visit, if needed.

Irrespective of whether release criteria have been met or not at the end of the last collection period on Day 31, no further sampling is planned.

For details on time points and procedures for the collection of blood, plasma, urine, and faeces samples, refer to [Flow Chart](#) and Section [5.3.2](#).

The safety measurements performed during the treatment period are specified in Section [5.2](#) of this protocol and in the [Flow Chart](#). AEs and concomitant therapy will be assessed continuously from obtaining the subject's written informed consent until the end of study examination.

For details on times of all of the trial procedures, refer to the [Flow Chart](#).

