10. The planned times for admission, discharge, as well as start and end of the collection intervals for urine and faeces are approximate. The procedures are to be performed within a time window of ± 4 h to the planned time.
11. Subjects are to collect faeces at home within 24 h intervals before being admitted to trial site for once-weekly in-house collection intervals. Home collection intervals: Day 15-16, 22-23, 29-30. If faeces are collected in the subsequent in-house collection interval, the faeces previously collected at home will be discarded. If no faeces are collected in the subsequent in-house collection interval (no defaecation) at the trial site, the faeces collected at home will be used instead for analysis.
12. For definition of the individual subject's end of trial see Section [6.2.3](#)
13. Drug and alcohol screening will be done at this time point.
14. Based on specific instructions provided, subjects will collect a pre-dose faeces sample at home in specific containers provided by the clinical trial site approximately 48 h before trial drug administration.
15. Confirmation of fitness includes physical examination, vital signs, ECG, recordings of AEs and concomitant therapies as well as evaluation of safety laboratory assessed on Day 8.
16. At this time point, only a sample for haematocrit measurement is taken.
17. PCR testing for SARS-CoV-2 will be performed at admission on Day – 1, Day 2 and at each admission to the trial site for the 24-h visits. Polymerase chain reaction testing for SARS-CoV-2 will be performed as needed based on the current status of the pandemic. SARS-CoV-2 testing on Day 2 may take place at any time during this day.
18. Metabolite profiling sampling times may be adapted based on information obtained during trial conduct (e.g., levels of radioactivity in each urine and/or plasma sample) as long as the overall blood volume stays the same.

FLOW CHART 2A (MICROTRACER HUMAN ADME)*

Visit	Day	Planned time (relative to first drug administration [h:min])	Approximate clock time of actual day [h:min]	Event and comment	Safety laboratory	Blood sampling for PK and total radioactivity ^{2,9}	PK ⁵ urine	PK ⁴ faeces	Blood sampling for metabolic profiling ¹⁸	12-lead ECG	Vital signs (BP, PR)	Questioning for AEs and concomitant therapy
1	-21 to -2			Screening (SCR) ¹	A ¹³			X ¹⁴		X	X	
2	-1	-18:00	14:00	Admission to trial site	B ^{13,17}		X ³					X
	1	-2:00	06:00			X ³			X ³	X ³	X ³	↑

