10. The planned times for admission, discharge, start and end of the urine and faeces collection intervals are approximate. The procedures are to be performed within a time window of ± 4 h to the planned time.
11. Subjects are to collect faeces at home within 24 h intervals before being admitted to trial site for once-weekly in-house collection, respectively. Home collection intervals: Day 15-16, 22-23, 29-30. If faeces are collected in the subsequent in-house collection interval, the faeces previously collected at home will be discarded. If no faeces are collected in the subsequent in-house collection interval (no defecation), the faeces collected at home will be used instead for analysis.
12. For definition of the individual subject's end of trial see Section [6.2.3](#)
13. Drug and alcohol screening will be done at this time point.
14. Subjects will collect a pre-dose faeces sample at home in specific containers provided by the clinical trial site approximately 48 h before trial drug administration.
15. Confirmation of fitness includes physical examination, vital signs, ECG, recordings of AEs and concomitant therapies as well as evaluation of safety laboratory assessed on Day 8.
16. At this time point, only a sample for haematocrit measurement is taken.
17. PCR testing for SARS-CoV-2 will be performed at admission on Day – 1, Day 2 and at each admission to the trial site for the 24-h visits. Polymerase chain reaction testing for SARS-CoV-2 will be performed as needed based on the current status of the pandemic. SARS-CoV-2 testing on Day 2 may take place at any time during this day.
18. Metabolite profiling sampling times may be adapted based on information obtained during trial conduct (e.g., levels of radioactivity in each urine and/or plasma sample) as long as the overall blood volume stays the same.

FLOW CHART 2B (MICROTRACER HUMAN ADME)*

Visit	Day	Planned time (relative to first drug administration [h:min])	Approximate clock time of actual day [h:min]	Event and comment	Safety laboratory	Blood sampling for PK and total radioactivity ²	Blood sampling for metabolic profiling ¹⁰	12-lead ECG	Vital signs (BP, PR)	Questioning for AEs and concomitant therapy
1	-21 to -2			Screening (SCR) ¹	A ⁷			x	x	
2	-1	-18:00	14:00	Admission to trial site	B ^{7,9}					x
	1	-2:00	06:00			x ³	x ³	x ³	x ³	↑
		0:00	08:00	Drug administration [REDACTED] BI 764198 (C-14) ([¹⁴ C]-labelled [REDACTED]) (treatment 2) ⁶						
		0:30	08:30			x				
		1:00	09:00			x	x			

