7.2.2 Primary endpoint analyses

The primary endpoints (refer to Section [2.1.2](#)) will be calculated according to the relevant BI internal procedures. The analysis will be descriptive in nature and based on the PKS.

To avoid underestimation of the total recovery of [^{14}C] in subjects who do not meet release criteria on Day 10, the excretion during the non-sampling phase of the study will be estimated using linear interpolation between the observed 24-h sampling periods before and after the non-sampling period for urine and faeces.

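### Replacing an empty in-house 24 h by the preceding home collection biases the late faecal rate behind fe_faeces upwards, by up to about 2-fold, in recalled subjects who do not reliably defaecate daily

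*Protocol*

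**What the plan says.** Subjects in cohorts 1 and 2a who have not met the release criteria by Day 10 return for "up to three additional 24 h in-house periods for the collection of urine and faeces" (Protocol 6.2.2). Each in-house day follows a 24 h home collection of faeces (Flow Chart 1, footnote 11: "Home collection intervals: Day 15-16, 22-23, 29-30").

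The two collections are not combined. The home sample "will be used as a back-up option for analysis in case no defaecation occurs" in the in-house day (6.2.2). In that case, per Flow Chart 1 footnote 11, "the faeces collected at home will be used instead for analysis". Otherwise it is not used: "If faeces are collected in the subsequent in-house collection period, the faeces previously collected at home will be discarded" (6.2.2; likewise Flow Chart 2A, footnote 11: "the faeces previously collected at home will be discarded").

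Protocol 7.2.2 fills the unsampled weeks "using linear interpolation between the observed 24-h sampling periods before and after the non-sampling period for urine and faeces", and SAP 5.1 repeats this. Neither document says how many hours a substituted home stool represents, that an empty in-house day may count as zero, or that results will be shown without substitution. SAP 7.4.4 lists no supplementary analysis.

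**The concern.** A 24 h faecal collection estimates the daily excretion rate without bias only if empty days count as zero. A stool passed after an interval longer than a day carries more than a day's excretion, and the empty days balance it. Here an empty in-house day is replaced by an earlier non-empty one, so part of that balance is removed, while an empty home day is never used to offset a full in-house stool.

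The resulting amount is more than a single data point. It anchors the interpolation across about six unsampled days on either side, so an error in it is multiplied in fe_faeces and in total recovery. Section 7.2.2 introduces interpolation to avoid underestimating recovery; this rule puts an upward error into that correction. The same amount also enters both release criteria in Section 3.1.

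**Working it through.** The documents give no bias figure to reproduce, so the rule is worked through directly.

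**Inputs from the Flow Charts.** Home windows: 341-365, 509-533 and 677-701 h. In-house windows: 365-389, 533-557 and 701-725 h. All last 24 h. Gaps between in-house sampling periods: 365 − 216 = 149 h, 533 − 389 = 144 h, 701 − 557 = 144 h.

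**Assumptions not in the documents.** The interval T between stools and the late faecal rate; steady excretion across the two windows, each stool carrying the excretion since the previous one; and a 24 h denominator for a substituted stool, inferred from the wording of 7.2.2.

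**Bias factor.** In units of one hour's excretion:

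E[rule] = E[in-house] + E[home, when in-house is empty]

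The first term is 24, the true value. The second is never negative and cannot exceed E[home] = 24, so the factor lies between 1 and 2. For regular stools:

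- T ≤ 24 h: the in-house day is never empty; factor 1.
- 24 < T ≤ 48 h: the in-house day is empty with probability 1 − 24/T, and the home day then holds one stool of size T. The second term is T − 24; factor T/24.
- T > 48 h: the home day holds a stool (and the in-house day is then empty) with probability 24/T. The second term is 24; factor 2.

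Simulation agrees and extends this to irregular timing:

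| Stool pattern | Factor |
|---|---|
| Regular, 12, 20 or 24 h | 1.00 |
| Regular, 30 h | 1.25 |
| Regular, 36 h | 1.50 |
| Regular, 48, 60 or 72 h | about 2.00 |
| Mean 24 h, CV 15 / 30 / 50% | 1.08 / 1.16 / 1.24 |
| Mean 36 h, CV 30% | 1.50 |
| Mean 48 h, CV 30% | 1.78 |

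**Effect on fe_faeces, one inflated anchor.** Assume a true rate of 0.5% of dose per day at Day 16. Factor 2 raises the anchor by 0.5:

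- observed day: 0.5
- Day 10-16 gap: 0.5 × 0.5 × 149/24 = 1.55; running total about 2.05 points of dose after one recall
- Day 17-23 gap, if there is a second recall: 0.5 × 0.5 × 144/24 = 1.50; total about 3.55

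Factor 1.5 gives half: about 1.03 and 1.78. In a cohort with 6 to 8 evaluable subjects, one subject with an excess of 3.55 moves the mean by 3.55/8 = 0.44 to 3.55/6 = 0.59 points.

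**Effect with every late anchor inflated.** With an assumed Day 10 rate of 1% per day and a half-life of 7 days, factor 1.5 adds 1.1 points after one recall and 3.0 after three; factor 2 adds 2.1 and 6.0. Over Day 10 rates of 0.5-2% per day, half-lives of 3-14 days and factors of 1.25-2, the excess runs from 0.1 to 20 points. The top needs every assumption at its extreme and three recalls. These figures compare with the same interpolation at factor 1, so they isolate the substitution.

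**Alternatives simulated.** Combining both windows over 48 h, or using the in-house day alone with empty days as zero, gives a factor of about 1.00 at every interval tried. Keeping the rule but dividing a substituted stool by 48 h only halves the bias (1.25 at 36 h, 1.50 at 48 h).

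**The case against.** Preferring supervised collection, with home collection as back-up, is a defensible choice, and routine use of home stools risks under-collection, which biases downwards. The trial is descriptive, and Protocol Section 1 says most subjects met the release criteria on Day 10. Protocol 7.2.2 leaves the calculation to internal procedures and 5.3.2.3 records exact collection times, so a longer denominator might be applied in practice. All of this stands and limits the reach of the point. It does not remove the point: as written, the substituted value has no other denominator, and even 48 h would leave half the bias.

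Several stronger readings are tempting and unsupported:

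- **That an over-full stool is always selected.** With regular daily stools it never is. Certainty holds only for regular intervals above 24 and up to 48 h. At 60 and 72 h the probability falls to 0.80 and 0.66, because both windows can be empty.
- **That discarding the home stool causes the bias.** In-house stool alone, with empty days as zero, is unbiased. The cause is conditional substitution, combined with the apparent 24 h denominator.
- **That the rule causes needless readmissions.** A larger amount makes the <1% criterion harder and the ≥90% criterion easier to meet, so the net effect is undetermined. The first recall cannot come from this rule, since the Day 10 decision rests on continuous in-house collection.
- **That 3.55 points is a typical error.** It needs a second recall, a factor of 2 and an assumed late rate.

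**Conclusion.** The point holds in a limited form. For cohort 1 and 2a subjects recalled after Day 10, the substitution rule biases the expected late faecal rate in one direction, upwards: by T/24 for regular stool intervals of 24-48 h, by at most about 2-fold, and by nothing for regular stools at least daily. Stools that average one a day but vary in timing still give some bias. The error carries into fe_faeces through the interpolation.

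The direction follows from the stated rule and the apparent 24 h denominator. The size in points of dose does not: it depends on stool interval and late excretion rate, which the documents do not give. Because the affected subjects are a minority of two 8-subject cohorts, this is a correction worth making rather than a threat to the trial's main conclusions.

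**What to change.** **Sampling rule (footnote 11 of Flow Charts 1 and 2A, and Section 6.2.2).** Assay both home and in-house faeces at each weekly visit. Take (home + in-house) / actual collection hours × 24 as the daily faecal rate, with empty windows counted as zero. Use that rate for the interpolation anchor and the <1% check. The home hours are then observed, and each interpolated faecal gap shortens by 24 h (149 to 125 h, 144 to 120 h). The cost is at most three extra faecal assays per recalled subject, on stools the plan already has subjects collect, plus reliance on complete home collection.

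**Analysis rule (SAP 5.1 and 7.4).** Protocol version 3.0 already reports Day 10 release results for these cohorts, and the SAP is dated later, so some home stools may be gone. For those subjects, state that an empty in-house 24 h counts as zero, flag every substituted stool, and report fe_faeces with and without the substitution. This costs one extra table. A single in-house day with zeros is unbiased, but it discards the home information.

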6.2.3 Follow-up period and trial completion

For AE assessment, laboratory tests, recording of ECG and vital signs, and physical examination during the follow-up period, see Section [5.2](#).

Subjects who discontinue the study before the planned end should undergo the EoS Visit.

If needed in the opinion of the investigator, additional visits may be scheduled after the EoS Visit for continued safety monitoring.

All abnormal values (including laboratory parameters) that are assessed as clinically relevant by the investigator will be monitored using the appropriate tests until a return to a medically acceptable level is achieved. (S)AEs persisting after a subject's EoS Visit must be followed until they have resolved, have been sufficiently characterised, or no further information can be obtained.

7. STATISTICAL METHODS AND DETERMINATION OF SAMPLE SIZE

7.1 NULL AND ALTERNATIVE HYPOTHESES

No confirmatory analysis will be conducted for this study. Data will be reported with descriptive statistics only.

7.2 PLANNED ANALYSES

7.2.1 General considerations

Subjects in cohort 2b receive the same treatment, using the same approach as for subjects in cohort 2a. However, for subjects in cohort 2b fewer endpoints are determined compared with cohort 2a, see Table 7.2.1 below.

Table 7.2.1: Overview of endpoints determined per cohort

Endpoints	Cohort 1	Cohort 2a	Cohort 2b
Primary endpoints	yes	yes	no
Secondary endpoints	yes	yes	yes
Further endpoints regarding			
Pharmacokinetic	yes	yes	yes*
Safety	yes	yes	yes

* Further PK endpoints for cohort 2b will be calculated as appropriate based on the available assessments.

In general, the descriptive analysis will be done by cohort: cohort 1, cohort 2a, cohort 2b and in addition for a general assessment of the microtracer approach, based on pooled data from cohorts 2a and 2b.

7.2.1.1 Analysis sets

Statistical analyses will be based on the following analysis sets:

- Treated set (TS): The treated set includes all subjects who were treated with at least one dose of trial drug. The treated set will be used for safety analyses.
- Pharmacokinetic parameter analysis set (PKS): This set includes all subjects in the treated set (TS) who provide at least one PK endpoint that was defined as primary or secondary and was not excluded due to a protocol deviation relevant to the evaluation of PK or due to PK non-evaluability (as specified in the following subsection 'Pharmacokinetics'). Thus, a subject will be included in the PKS, even if he contributes only one PK parameter value for one period to the statistical assessment. Descriptive analyses of PK parameters will be based on the PKS.

Descriptions of additional analysis sets may be provided in the TSAP.

Adherence to the protocol will be assessed by the trial team. Important protocol deviation (iPD) categories will be suggested in the IPD specification file. IPDs will be identified no later than in the Report Planning Meeting, and the iPD categories will be updated as needed.

7.2.1.2 Pharmacokinetics

The pharmacokinetic parameters listed in Section [2.1](#) and [2.2.2](#) for drug BI 764198 will be calculated according to the relevant BI internal procedures.

Plasma, urine and faeces concentration data and parameters of a subject will be included in the statistical pharmacokinetic (PK) analyses if they are not flagged for exclusion due to a protocol deviation relevant to the evaluation of PK (to be decided no later than in the Report Planning Meeting) or due to PK non-evaluability (as revealed during data analysis, based on the criteria specified below). Exclusion of a subject's data will be documented in the CTR.

Important protocol deviations may be

- Incorrect trial medication taken, i.e., the subject received at least one dose of trial medication the subject was not assigned to
- Incorrect dose of trial medication taken
- Use of restricted medications

Plasma, urine and faeces concentrations and/or parameters of a subject will be considered as non-evaluable, if for example

- The subject experienced emesis that occurred at or before two times median t_{\max} of the respective treatment (Median t_{\max}).
- Missing samples/concentration data at important phases of PK disposition curve

Plasma, urine, faeces and if applicable vomiting concentration data and parameters of a subject which are flagged for exclusion will be reported with its individual values but will not be included in the descriptive statistics.

Only concentration values within the validated concentration range and actual sampling times will be used for the calculation of pharmacokinetic parameters. Concentrations used in the pharmacokinetic calculations will be in the same format provided in the bioanalytical report (that is, to the same number of decimal places provided in the bioanalytical report).

7.2.2 Primary endpoint analyses

The primary endpoints (refer to Section [2.1.2](#)) will be calculated according to the relevant BI internal procedures. The analysis will be descriptive in nature and based on the PKS.

To avoid underestimation of the total recovery of [^{14}C] in subjects who do not meet release criteria on Day 10, the excretion during the non-sampling phase of the study will be estimated using linear interpolation between the observed 24-h sampling periods before and after the non-sampling period for urine and faeces.

7.2.3 Secondary endpoint analyses

The secondary endpoints (refer to Section [2.1.3](#)) will be calculated according to the relevant BI internal procedures and will be assessed statistically using the same methods as described for the primary endpoints.

[REDACTED]

7.2.5 Safety analyses

Safety will be analysed based on the assessments described in Section [2.2.2.2](#). All treated subjects (TS, refer to Section [7.2](#)) will be included in the safety analysis. Safety analyses will be descriptive in nature and based on BI standards. No hypothesis testing is planned.

For all analyses, the treatment actually administered (= treatment at onset) to the subject will be used (any deviations from the assigned treatment will be discussed in the minutes of the Report Planning Meeting).

Treatments will be compared in a descriptive way. Tabulations of frequencies/proportions will be used to evaluate categorical (qualitative) data, and tabulations of descriptive statistics will be used to analyse continuous (quantitative) data.

Measurements (such as ECG, vital signs, or laboratory parameters) or AEs will be assigned to treatments (see Section [4.1](#)) based on the actual treatment at the time of the measurement or on the recorded time of AE onset (concept of treatment emergent AEs). Therefore, measurements performed or AEs recorded prior to first intake of trial medication will be assigned to the screening period, those between trial medication intake and end of REP (see Section [1.2.2](#)) will be assigned to the treatment period. Events occurring after the REP but prior to end of trial termination date will be assigned to 'follow-up'. These assignments including the corresponding time intervals will be defined in detail in the TSAP. Note that AEs occurring after the last per protocol contact but entered before database lock of the trial will be reported to Pharmacovigilance only and will not be captured in the trial database. Additionally, further treatment intervals (analysing treatments) may be defined in the TSAP.

Adverse events will be coded using the Medical Dictionary for Regulatory Activities (MedDRA). Frequency, severity, and causal relationship of AEs will be tabulated by treatment, system organ class, and preferred term. SAEs, AESIs (see Section [5.2.6.1](#)), and other significant AEs (according to ICH E3) will be listed separately.

Previous and concomitant therapies will be presented per treatment group without consideration of time intervals and treatment periods.

Laboratory data will be compared to their reference ranges. Values outside the reference range will be highlighted in the listings. Additionally, differences from baseline will be evaluated.

Vital signs or other safety-relevant data will be assessed with regard to possible on-treatment changes from baseline.

Vital signs data will be assessed with regard to possible on-treatment changes from baseline. Relevant ECG findings will be reported as AEs.

